6.4.1.2 Treatment Emergent Adverse Events

The following summaries will display the number and percentage of subjects with adverse events by system organ class (SOC) and preferred term (sorted alphabetically) for each treatment group and overall:

- All TEAEs

- Serious TEAEs
- TEAEs by Maximum Severity
- Study Drug Related TEAEs
- All AEs that lead to premature discontinuation from the study

An additional summary will tally the number and percent of subjects in each treatment group who experience an AE that occurs in at least 5% of subjects. The summary will be presented by preferred term in decreasing order of incidence.

The summaries will be provided for the double-blind treatment period. No inferential statistical methods (i.e., methods that yield p-values) will be used to compare treatment groups on the frequency or severity of AEs.

Additionally, the following listings will be produced for all enrolled subjects:

- All AEs, events considered to be TEAE will be identified in the listing
- Serious AEs
- AEs that lead to premature discontinuation from the study
- Deaths

6.4.2 Adverse Events of Special Interest (AESI)

As per ICH guidance ([E2F Development Safety Update Report \[2011\]](#)), the sponsor has identified the following AESIs for the ZX008 in below table (Table 14 of protocol)-

Table 5 – Adverse Events of Special Interest:

Metabolic/Endocrine
1. Elevated prolactin level $\geq 2x$ above the upper limit of normal (ULN)
Neuropsychiatric
1. Suicidal thoughts, ideation or gestures

All adverse events of special interest will be listed separately.

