Subjects with positive findings on ECHO, ECG and/or physical examination should continue to be followed until the finding is resolved or stable and unlikely to change, with reports submitted as AESI to the ZX008 safety database.

Table 10. Schedule of Post-Treatment Cardiac Follow-up

Parameter	Duration of Blinded ^a or Fenfluramine Treatment				Have had any cardiac sign or symptom regardless of the time on study drug ^b
	Less than 2 weeks Cumulative	2 to 4 weeks	> 4 and < 13 weeks	> 13 weeks	
ECHO	No	Yes, 3 months post-treatment	Yes, 3 months post-treatment	Yes, 3-6 months post-treatment	Yes, 3 and 6 months post-treatment, and until resolved, or stable and unlikely to change
ECG	No	Yes, 3 months post-treatment	Yes, 3 months post-treatment	Yes, 3-6 months post-treatment	Yes, 3 and 6 months post-treatment and until resolved, or stable and unlikely to change
Physical examination	No	Yes, 3 months post-treatment	Yes, 3 months post-treatment	Yes, 3 months post treatment only	Yes, 3 and 6 months post-treatment, and until resolved, or stable and unlikely to change

ECG = electrocardiogram; ECHO = echocardiogram; IPCAB = International Pediatric Cardiology Advisory Board

^a If blind is broken at the end of the study and a subject revealed to have taken only placebo, no further testing is required.

^b Positive sign or symptom includes any development of valve thickening or regurgitation “trace” or greater in mitral, aortic, mild or greater in pulmonary, tricuspid), or sign or symptom indicative of potential pulmonary hypertension as adjudicated by the IPCAB.

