8.1.3 Adverse Events of Special Interest

As per ICH guidance ([E2F Development Safety Update Report 2011](#)), the Sponsor has identified the following AESI for the ZX008 program ([Table 14](#)).

Table 14. Adverse Events of Special Interest

Metabolic/Endocrine
1. Elevated prolactin level $\geq 2x$ above the upper limit of normal (ULN)
2. Hypoglycemia – serum blood glucose more than 20% below the glucose level on Day -1 value or more than 10% below LLN (reference range 60 – 140 mg/dL)
Neuropsychiatric
13. Suicidal thoughts, ideation or gestures
LLN = lower limit of normal; ULN = upper limit of normal

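### The SAP's list of adverse events of special interest omits hypoglycemia, although it cites the protocol table that includes it, and the change is not declared

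*SAP*

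**What the plan says.** Protocol 8.1.3 introduces Table 14 with the words "the Sponsor has identified the following AESI for the ZX008 program". As supplied, the table has two metabolic/endocrine items and one neuropsychiatric item. The first is prolactin at least twice the upper limit of normal. The second is "Hypoglycemia – serum blood glucose more than 20% below the glucose level on Day -1 value or more than 10% below LLN", with a reference range of 60 to 140 mg/dL. The third is "Suicidal thoughts, ideation or gestures". The protocol synopsis (Statistical Methods, Safety) asks for AESIs to be summarized on their own, in the same way as other adverse events.

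SAP 6.4.2 states that "the sponsor has identified the following AESIs for the ZX008 in below table (Table 14 of protocol". Its table, labelled Table 5 in that section (the SAP's schedule of assessments carries the same number), has one metabolic/endocrine row, for prolactin, and one neuropsychiatric row, for suicidality. The section promises a separate AESI listing. SAP Appendix 1 plans Table 14.3.1.8b (overview), Table 14.3.1.9b (by system organ class and preferred term) and Listing 16.2.7.2b.

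SAP 6.9 declares two safety changes, one to the summary period and one to the treatment grouping. It declares none to the AESI list.

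**The concern.** A table presented as a copy of the protocol's list lacks one of its entries. That is either a slip or an undeclared decision, and a reader of the SAP cannot tell which. Section 6.4.2 is the only place where the SAP defines an AESI, and no section gives a glucose threshold for hypoglycemia. A programmer working from the SAP alone would have no reason to flag hypoglycemia.

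What is at stake is a comparison by arm of subjects who meet a safety criterion fixed in the protocol. The protocol treats low glucose as worth attention elsewhere too: section 5.7 asks investigators to consider hypoglycemia and weight loss in subjects on glucose-lowering drugs.

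**Working it through.** The plan states no figure to reproduce, so the check compares the two lists and then asks whether another output covers the gap.

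**1. The lists side by side**

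| Item | Protocol 8.1.3, Table 14 | SAP 6.4.2, Table 5 |
|---|---|---|
| Elevated prolactin | present | present |
| Hypoglycemia | present | absent |
| Suicidality | present | present |

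One item is missing: 3 − 2 = 1.

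**2. Is the change declared?** SAP 6.9 contains no entry on the AESI list.

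**3. Which outputs depend on the list?** Three AESI outputs are planned (Tables 14.3.1.8b and 14.3.1.9b, Listing 16.2.7.2b). The SAP does not say whether they select events by its Table 5 or by the AESI record that sites complete at visits (protocol 6.2.2 to 6.2.5.11; AESI row of the SAP schedule).

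**4. Does another output apply the protocol's definition?** The first part of that definition is relative: "serum blood glucose more than 20% below the glucose level on Day -1 value". Using the stated lower limit of 60 mg/dL:

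- The absolute part is met below 0.90 × 60 = 54 mg/dL.
- The relative part is met below 0.80 × G, where G is the Day -1 glucose. That boundary lies above 60 mg/dL whenever G > 60 / 0.80 = 75 mg/dL.
- Example: a fall from 120 to 95 mg/dL is (120 − 95) / 120 = 20.8%. It meets the protocol's criterion while 95 is well inside the reference range.

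Set against that example, the remaining outputs do the following:

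- **General adverse event tables and listings (SAP 6.4.1.2).** Protocol 7.2.5 and 8.1.1 require a laboratory result to be recorded as an adverse event when the investigator judges it clinically significant. An in-range fall need not be recorded.
- **Biochemistry summaries (SAP 6.4.9).** These give observed values and changes from baseline by arm. They do not count subjects who cross the 20% boundary.
- **Potentially clinically significant listing (SAP 6.4.9).** This uses sponsor alert ranges that are not stated to match Table 14.
- **Extreme-value listing (SAP 6.4.9).** This shows out-of-range values, so 95 mg/dL would not appear.
- **Full laboratory listing.** This would show the value, unflagged against the protocol's rule.

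The raw information therefore survives, but no output outside the AESI set is stated to count subjects by arm under the protocol's definition.

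**The case against.** The strongest reply is that nothing is lost from the study report. Reported hypoglycemia stays in the general adverse event tables, and glucose is summarized by arm and listed in full. Sites also record AESIs under the protocol, so if the AESI outputs use that record, hypoglycemia events could still appear. This stands. A reader might infer that hypoglycemia will be absent from every AESI table and listing. The documents do not support that, because the SAP never says which source drives those outputs. That silence is part of what needs correcting.

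A second reply is version mismatch. SAP 6.9 describes a protocol with about 70 subjects, a 40% responder endpoint and a log-rank test. The protocol supplied, Amendment 3.3 (US/CAN), has about 90 subjects, no 40% responder endpoint and a Wilcoxon test. The SAP may have been written against another version. That may explain the omission but does not cure it. The SAP is dated 25 June 2018, after the 2 February 2018 amendment, and what Table 14 contained in any other version cannot be checked here.

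A third reply is text extraction. The protocol table's numbering runs 1, 2, 13, so rows may have been lost there. That could change the total number of protocol items but cannot remove hypoglycemia from the protocol. For the same reason, a reader should not infer that a fixed fraction of the AESIs is missing: the total is uncertain, and rows are neither events nor subjects. A row lost from the SAP table cannot be wholly excluded, but its numbering starts at 1 under each heading and shows no break.

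Finally, a reader might infer that the SAP also drops cardiac AESIs, since protocol 6.2.6 has positive cardiac follow-up findings followed up "with reports submitted as AESI to the ZX008 safety database". The documents do not support adding that here. Protocol Table 14 as supplied has no cardiac item, so the SAP does not depart from it on this. SAP 3.2 sends cardiac follow-up results elsewhere, and SAP 6.4.7 sends ECHO results to a separate report.

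**Conclusion.** The mismatch is real and undeclared, and it is limited to one item: hypoglycemia is in protocol Table 14 and absent from the SAP table that cites it. Whether the three AESI outputs would omit it depends on their following the SAP's table, which the SAP does not settle. If they do, no planned output is stated to report the protocol's hypoglycemia criterion by arm. The underlying glucose and adverse event data remain available in other outputs. Sample size, the testing hierarchy and the efficacy conclusions are untouched. The conclusion assumes that the two tables are complete as supplied with respect to hypoglycemia. It does not rely on the protocol's amendment summary, which words the glucose criterion differently. This should be corrected because it concerns a pre-specified safety category and costs little, but it does not threaten the trial's main result.

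**What to change.** 1. Reconcile the table in SAP 6.4.2 with protocol Table 14. Either add hypoglycemia exactly as the protocol defines it, or keep it out and declare and justify the removal in SAP 6.9.
2. State for Tables 14.3.1.8b and 14.3.1.9b and Listing 16.2.7.2b whether AESIs come from the site AESI record, a derivation from laboratory values, or both. If both, say how a subject identified by only one source is shown. The choice matters because an in-range fall can meet the relative criterion without being reported by the site.
3. If a derivation is used, name the reference value. The protocol specifies Day -1, while SAP 6.1.4 takes the last non-missing result before first dose. The two can differ when the Day -1 sample is missing.
4. Name the protocol version against which SAP 6.4.2 and 6.9 were written.

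The cost is SAP wording plus at most one small programmed derivation. Glucose is part of the scheduled chemistry panel at Day -1 and Days 22, 50, 78 and 106, so no new data are needed. The change should be made before unblinding.

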6.4.3 Physical Examination

A complete physical examination will be performed at Screening Visit (Visit 1), day of randomization (visit 3) prior to first dose of study medication, end of study (EOS) visit, and at the Cardiac follow-up visit for patients who do not enter the open-label extension study. An abbreviated physical exam is performed at Day 15 (Visit 5), 22 (Visit 6), 50 (Visit 8), 78 (Visit 10) and at the Cardiac follow-up visit for patients who do not enter the open-label extension study.

All physical examination results will be presented in a subject data listing, including the description of abnormalities. New, clinically meaningful abnormalities are reported as adverse events.

6.4.4 Neurological Examination

A complete neurological examination will be performed at Screening Visit (Visit 1) and EOS (Visit 12).

All neurological examination results will be presented in a subject data listing including the description of abnormalities.

6.4.5 Vital Signs, Weight, and BMI

Vital signs data including blood pressure, heart rate, temperature, respiratory rate, weight, and BMI will be documented for subjects during study at screening visit (visit 1), randomization (visit 3) prior to first dose of study medication, titration period (visit 5 and visit 6), and maintenance period (visit 8 and visit 10) and at EOS visit (visit 12).

The mean values and change from baseline to each on-study visit time point evaluation will be summarized for vital signs and weight by treatment group. Vital signs, Weight and BMI data will be presented for each patient in a data listing. The most extreme abnormal values for each subject will also be listed.

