1.2 BACKGROUND INFORMATION ON STUDY PRODUCT

Zogenix has developed an oral solution formulation of fenfluramine hydrochloride, ZX008, for the adjunctive treatment of seizures in Dravet syndrome. In addition, the effects of ZX008 on a composite of symptoms that negatively impact quality of life and intellectual development will be explored. Fenfluramine is an amphetamine analogue that was approved in a large number of countries and widely prescribed as an appetite suppressant for the treatment of adult obesity.

Products containing fenfluramine and the D-enantiomer were withdrawn from the market globally after reports of heart valve disease and pulmonary hypertension in the late 1990's ([Connolly 1997](#); [CDC 1997](#); [Wong 1998](#)). While the risk/benefit relationship for fenfluramine is thus considered unfavorable for the treatment of obesity in adults, establishing seizure control in Dravet syndrome or any of the catastrophic childhood epilepsies might lead to a more acceptable risk/benefit profile for fenfluramine, especially if lower doses can be used successfully.

As a result of this previous extensive use of fenfluramine, there is a large body of information in the public domain concerning its pharmacology, toxicology and use in the treatment of obesity ([ZX008 IB 2016](#)). There is also a large body of information concerning its clinical safety profile.

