4.1 INCLUSION CRITERIA

Subjects must meet all of the following inclusion criteria to be enrolled into the study:

1. Subject is male or non-pregnant, non-lactating female, age 2 to 18 years, inclusive as of the day of the Screening Visit. Female subjects of childbearing potential must not be pregnant or breast-feeding. Female subjects of childbearing potential must have a negative urine pregnancy test. Subjects of childbearing or child-fathering potential must be willing to use medically acceptable forms of birth control (see [Section 4.4](#)), which includes abstinence, while being treated on this study and for 90 days after the dose of study drug.
2. Subject must have documented medical history to support a clinical diagnosis of Dravet syndrome, where convulsive seizures are not completely controlled by current antiepileptic drugs.
3. Subjects must meet all of the following 5 criteria:
 - a. Onset of seizures in the first year of life in an otherwise healthy infant.
 - b. A history of seizures that are either generalized tonic-clonic or unilateral clonic or bilateral clonic, and are prolonged.
 - c. Initial development is normal.
 - d. History of normal brain magnetic resonance imaging (MRI) without cortical brain malformation.
 - e. Lack of alternative diagnosis.

4. Subjects must meet at least one of the following 3 criteria:
 - a. Emergence of another seizure type, including myoclonic, generalized tonic-clonic, tonic, atonic, absence and/or focal has developed after the first seizure type.
 - b. Prolonged exposure to warm temperatures induces seizures and/or seizures are associated with fevers due to illness or vaccines, hot baths, high levels of activity and sudden temperature changes and/or seizures are induced by strong natural and/or fluorescent lighting, as well as certain visual patterns.
 - c. Genetic test results consistent with a diagnosis of Dravet syndrome (pathogenic, likely pathogenic, variant of unknown significance, or inconclusive but unlikely to support an alternative diagnosis.)
5. Subject must have had \geq 4 convulsive seizures (tonic-clonic, tonic, clonic) per 4-week period for 12 weeks prior to screening, by parent/guardian report to investigator or investigator medical notes (**Cohort 2 only**).
6. All medications or interventions for epilepsy (including ketogenic diet [KD] and vagal nerve stimulation [VNS]) must be stable for at least 4 weeks prior to screening and are expected to remain stable throughout the study.

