6.1.3 Subgroups

Select efficacy and safety outputs may be further broken down by the following subgroups:

- Age strata: <6 years, ≥ 6 years

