Table	14.3.1.4b	Serious TEAEs by Primary SOC and PT – Safety Population
Table	14.3.1.5b	Study Drug Related TEAEs by Primary SOC and PT – Safety Population
Table	14.3.1.6b	TEAEs by Maximum Severity by Primary SOC and PT – Safety Population
Table	14.3.1.7b	Treatment-Emergent Adverse Events Occurring in $\geq 5\%$ of Subjects by MedDRA System Organ Class and Preferred Term - Safety Population
Table	14.3.1.8b	Overview of Number of Subjects with Treatment-Emergent Adverse Events of Special Interest (AESI) – Safety Population
Table	14.3.1.9b	Adverse Events of Special Interest (AESI) by MedDRA System Organ Class and Preferred Term – Safety Population
	14.3.2	Listings of Deaths, Other Serious and Significant Adverse Events

Table	14.3.2.1b	Listing of Deaths – Safety Population
Table	14.3.2.2b	Listing of SAEs – Safety Population
Table	14.3.2.3b	Listing of Discontinuations Due to AE – Safety Population
	14.3.4	Laboratory value
Table	14.3.4.1b	Laboratory Parameters – Hematology – Safety Population
Table	14.3.4.2b	Laboratory Parameters – Biochemistry – Safety Population
Table	14.3.4.4.1b	Laboratory Parameters – Urinalysis (Quantitative Parameters) – Safety Population
Table	14.3.4.4.2b	Laboratory Parameters – Urinalysis Categorical – Safety Population
Table	14.3.4.5b	Tests of Growth, Precocious Puberty and Thyroid Function – Safety Population
Table	14.3.4.6b	Epilepsy Genotype Panel – Safety Population
	14.4.1	Vital Signs
Table	14.4.1.1b	Vital Signs Parameters – Safety Population
	14.4.4	Tanner Staging
Table	14.4.4.1b	Tanner Staging by Age Group for Boys – Safety Population
Table	14.4.4.2b	Tanner Staging by Age Group for Girls – Safety Population
	14.4.5	Columbia-Suicide Severity Rating Scale (C-SSRS)
Table	14.4.5.1b	Columbia Suicide Severity-Rating Scale (C-SSRS) - Number of Subjects with Suicidal Ideation, Suicidal Behavior, and Self-Injurious Behavior without Suicidal Intent based on the C-SSRS – Safety Population
Table	14.4.5.2b	Columbia Suicide Severity-Rating Scale (C-SSRS) - Shift Table of Changes in C-SSRS Categories During Treatment - Safety Population
	14.4.6	Brief Rating Inventory of Executive Function- (BRIEF)
Table	14.4.6.1b	Brief Rating Inventory of Executive Function Preschool Version (BRIEF-P) – Safety Population
Table	14.4.6.2b	Brief Rating Inventory of Executive Function (BRIEF) – Safety Population
	16.2	Subject data listing
	16.2.1	Subject disposition and discontinuation
Listing	16.2.1.1b	Subject Completion/Discontinuation
	16.2.2	Protocol deviations

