Listing	16.2.2b	Major Protocol Deviations

	16.2.3	Subjects excluded from analysis
Listing	16.2.3.1b	Subjects Excluded from the Per Protocol Population
Listing	16.2.3.2b	Subject Allocation to Trial Populations
	16.2.4	Demographic data and other baseline characteristics
Listing	16.2.4.1.1b	Demographic and Baseline Characteristic Data
Listing	16.2.4.1.2b	Percentage Change from Baseline in Weight and BMI
Listing	16.2.4.2b	Medical History
Listing	16.2.4.3b	Prior and Concomitant Medications and Therapies/Treatments
Listing	16.2.4.4b	Prior and Concomitant Anti-Epileptic Drugs (AEDs)
Listing	16.2.4.5b	Rescue Medications
	16.2.5	Treatment exposure and compliance
Listing	16.2.5.1b	IMP Intake per Day during Treatment
Listing	16.2.5.2b	IMP Intake – Self Reported % Compliance
Listing	16.2.5.3b	Drug Accountability and Compliance to Study Treatment by Visit
	16.2.6	Efficacy data
Listing	16.2.6.1b	Convulsive Seizure – Duration and Number of Occurrences per Subject (Diary data)
Listing	16.2.6.2b	Non-Convulsive Seizure – Duration and Number of Occurrences per Subject (Diary data)
Listing	16.2.6.3b	Longest Interval between Convulsive Seizures during T+M, and Convulsive Seizure Free Days during Baseline, M and T
Listing	16.2.6.4b	Percent Change in Convulsive Seizure Frequency from Baseline
Listing	16.2.6.5b	Clinical Global Impression – Improvement Rating as Assessed by the Parent/Caregiver and Investigator
Listing	16.2.6.6b	Quality of Life in Childhood Epilepsy Scale
Listing	16.2.6.7b	Quality of Life of the Parent/Caregiver using EQ-5D-5L Scale
Listing	16.2.6.8.1b	Pediatric Quality of Life Inventory (Peds QL) - for TODDLERS (age 2-4 years)
Listing	16.2.6.8.2b	Pediatric Quality of Life Inventory (Peds QL) - for Young Children (age 5-7 years)
Listing	16.2.6.8.3b	Pediatric Quality of Life Inventory (Peds QL) - for Children (age 8-12 years)
Listing	16.2.6.8.4b	Pediatric Quality of Life Inventory (Peds QL) - for TEENS (age 13-18 years)
Listing	16.2.6.8.5b	Pediatric Quality of Life Inventory (Peds QL) – Family Impact Module

Listing	16.2.6.9b	Sleep Quality and Meal Time Behavior
Listing	16.2.6.10b	Karolinska Sleepiness Scale
Listing	16.2.6.11b	Hospitalization and Other Healthcare Resource Utilization to Treat Seizure
	16.2.7	Adverse events
Listing	16.2.7.1b	Adverse Events
Listing	16.2.7.2b	Adverse Events of Special Interests (AESI)
	16.2.8	Laboratory data
Listing	16.2.8.1.1b	Laboratory Data: Hematology Parameters

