Listing	16.2.8.1.2b	Extreme Value Laboratory Parameters - Hematology
Listing	16.2.8.2.1b	Laboratory Data: Biochemistry Parameters
Listing	16.2.8.2.2b	Extreme Value Laboratory Parameters - Biochemistry
Listing	16.2.8.3b	Laboratory Data: Coagulation Parameters
Listing	16.2.8.4.1b	Laboratory Data: Urinalysis Parameters
Listing	16.2.8.4.2b	Extreme Value Laboratory Parameters - Urinalysis
Listing	16.2.8.5b	Tests of Growth, Precocious Puberty and Thyroid Function
Listing	16.2.8.6b	Urine Pregnancy Test
Listing	16.2.8.7b	Urine Cannabinoid Panel
Listing	16.2.8.8b	Whole Blood Cannabidiol
	16.2.9	Other Safety Data
Listing	16.2.9.1.1b	Vital Signs
Listing	16.2.9.1.2b	Most Extreme Abnormal Vital Signs Data
Listing	16.2.9.1.3b	Subjects with Weight Decreases >5% During Treatment
Listing	16.2.9.2b	Listing of Items on Columbia-Suicide Severity Rating Scale
Listing	16.2.9.3.1b	Behavior Rating Inventory of Executive Function – Preschool Version (BRIEF-P) – Individual Questions
Listing	16.2.9.3.2b	Behavior Rating Inventory of Executive Function (BRIEF) – Individual Questions
Listing	16.2.9.4b	Tanner Staging
Listing	16.2.9.5b	Physical Examination
Listing	16.2.9.6b	Neurological Examination
Listing	16.2.9.7b	Epilepsy Genotype Panel
Listing	16.2.10.1b	Individual Subject Drug Concentrations for Background AED
Listing	16.2.10.2b	Individual Subject Drug Concentrations for ZX008

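### Weight is summarised by arm only as observed values and change from baseline; percentage change and loss above 5% are planned as listings, so neither is tabulated by arm

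*SAP*

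**What the plan says.** The safety objective for Cohort 2 (Protocol 2.3, SAP 2.4) is comparative and includes body weight, and Protocol 2.5.2 lists body weight as a safety endpoint.

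SAP 6.4.5 gives the by-arm analysis: "The mean values and change from baseline to each on-study visit time point evaluation will be summarized for vital signs and weight by treatment group". For individual data it adds: "Vital signs, Weight and BMI data will be presented for each patient in a data listing". BMI is missing from the first sentence and appears only in the second. The one table in SAP Appendix 1 whose title matches is 14.4.1.1b, "Vital Signs Parameters – Safety Population".

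Two relative measures appear in Appendix 1, both as listings:
- Listing 16.2.4.1.2b: "Percentage Change from Baseline in Weight and BMI"
- Listing 16.2.9.1.3b: "Subjects with Weight Decreases >5% During Treatment"

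No table in Appendix 1 is titled for either quantity. On age breakdown, SAP 6.1.3 is permissive: "Select efficacy and safety outputs may be further broken down by the following subgroups", the subgroups being under 6 and 6 years or older. Weight is not named there.

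**The concern.** Weight loss is a foreseeable effect of this drug. Protocol 1.2 describes its former use as an appetite suppressant, and Protocol 1.3 reports reduced weight gain in the juvenile toxicology study. A reader of the safety results will therefore want to know how much weight subjects lost relative to their size, and how many in each arm lost a notable amount.

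The population is "age 2 to 18 years, inclusive as of the day of the Screening Visit", so body weights will differ several-fold. A mean or median change in kg over that range answers neither question. The sponsor has already chosen the measures that do, percentage change and a 5% threshold, but a listing does not compare arms. The report could meet its plan in full and still contain no table giving the number with a loss above 5% on ZX008 and on placebo.

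**Working it through.** The plan states no figure for weight: no expected loss, no SD, no power. There is nothing to reproduce. The sample size (45 per arm in Protocol 10.1, 40 per arm in SAP 6.1.10) is set for seizure frequency. Here it only shows that about 80 to 90 subjects are involved.

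**Step 1: which weight outputs are by arm.**

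| Quantity | By-arm table | Listing |
|---|---|---|
| Observed weight, change from baseline | 14.4.1.1b (SAP 6.4.5) | yes |
| Percentage change in weight and BMI | none titled | 16.2.4.1.2b |
| Decrease above 5% | none titled | 16.2.9.1.3b |

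**Step 2: the unit.** SAP 6.4.5 names none. SAP 6.2.3.1 records weight in kg, and percentage change is a separate output, so change in kg is the natural reading. It remains an inference.

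**Step 3: what a 5% loss is in kg.** Loss = 0.05 × weight. The documents give no weight distribution, so these weights are illustrative.

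| Weight (kg) | 5% loss (kg) |
|---|---|
| 12 | 0.6 |
| 20 | 1.0 |
| 40 | 2.0 |
| 60 | 3.0 |

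The range is 3.0 / 0.6 = 5-fold. Two weights implied by the protocol give a narrower range. Section 6.3 provides for subjects below 13.5 kg (0.05 × 13.5 = 0.675 kg), and the 20 mg/day maximum at 0.5 mg/kg/day is reached at 20 / 0.5 = 40 kg (2.0 kg). That is 2.0 / 0.675, about 3-fold.

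**Step 4: the reverse direction.** A loss of 1.0 kg is 100 × 1/12 = 8.3% at 12 kg, 5.0% at 20 kg and 100 × 1/60 = 1.7% at 60 kg. The same kg value lies above, on or below the SAP's threshold depending on the subject. The number losing more than 5% therefore cannot be recovered from any summary of kg change, whether mean, median or quartile.

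**The case against.** Much can fairly be said for the plan as written, and it rules out several stronger readings.

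- **A reader might infer that only means are given.** SAP 6.1.1 commits continuous data to n, mean, SD, median, quartiles and range. Medians and quartiles are less driven by a few heavy adolescents. This stands, but they are still in kg (step 4).
- **A reader might infer that the kg scale biases the comparison.** Randomisation is 1:1 and stratified by age (under 6, 6 or older), so weight distributions should be similar between arms. There is no ground for a claim of bias.
- **A reader might infer that kg is the less precise scale.** That holds if loss is proportional to weight and the SD is constant in percent. It can reverse if the SD is constant in kg. Assume log-normal weights with mean 30 kg and CV 0.5, a 3% loss, and an SD of change of 1.5 kg. The mean effect is 0.03 on both scales once kg change is divided by mean weight. The variance is then 1.5²/30² + 0.03² × 0.5² = 0.0027 on the kg scale, against 1.5² × (1 + 0.5²)³/30² = 0.0049 on the percentage scale. The documents support neither SD assumption, and SAP 6.4.5 plans no test for weight, so no precision claim is made here.
- **A reader might infer that losses above 5% go unreported.** Listing 16.2.9.1.3b covers these subjects, and with 80 to 90 subjects they can be counted by hand. What is missing is the tabulated comparison.
- **A reader might add that loss matters most in the smallest children.** The documents do not say so, and the point does not need it.

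The treatment-emergent adverse event tables (SAP 6.4.1.2) are a second by-arm route. They depend on what investigators report, not on measured weight against a set threshold, so they do not replace the missing rows. Finally, Appendix 1 gives titles only. Table 14.4.1.1b may be meant to hold more than its title shows, but the plan does not say so. Protocol 10.5.2 promises only an appropriate summary by treatment, so there is no departure from the protocol.

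**Conclusion.** The point holds as a minor one. For a comparative safety endpoint with a foreseeable drug effect, the SAP summarises weight by arm on a scale where the same relative loss differs about five-fold between 12 and 60 kg. The two relative measures it has already planned stay in listings. That rests on the text of SAP 6.4.5 and the titles in Appendix 1, and on reading the unit as kg. The five-fold figure also rests on the illustrative weights; the two weights implied by the protocol give about three-fold.

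No data are lost, no planned inference changes and the arms remain fairly compared. What is gained is a result that can be read across ages 2 to 18 and a stated count per arm of subjects losing more than 5%.

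**What to change.** In SAP 6.4.5 and Table 14.4.1.1b, add two descriptive summaries on the Safety Population:

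1. Percentage change in weight from baseline by arm and visit, overall and by age stratum (under 6, 6 years or older), with the SAP 6.1.1 statistics.
2. Number and percentage per arm with a decrease above 5% from baseline at any time in T+M.

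State the window. The listing title refers only to treatment, and the double-blind treatment period in SAP 6.1.6 includes taper and transition, whereas SAP 6.9 says safety is summarised for T+M. Baseline is already defined in SAP 6.1.4 as the last non-missing value before first dose.

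No test is needed. The variables are those already planned for Listings 16.2.4.1.2b and 16.2.9.1.3b, and no new data are collected. The cost is a few rows in one existing table.
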